4. RISKS AND BENEFITS OF THE INVESTIGATIONAL DEVICE AND CLINICAL TRIAL

The risks associated with use of the Optune™ System are principally electrical or mechanical failure leading to electrical shock, electromagnetic interference, as well as the risk that the treatment will not be effective in delaying tumor progression or causing regression. Additional risks include skin irritation, and skin breakdown or infection at electrode sites. Technical failure is extremely unlikely due to stringent compliance with all standard design and manufacturing safety protocols. In addition, appropriate measures have been taken to minimize the risk to study subjects, including preclinical *in vitro* and *in vivo* testing to ensure safe operation of the device.

The use of TTFields in glioblastoma has been used safely in combination with temozolomide after radiation therapy in EF-14. Although mild to moderate skin irritation was common (43%), severe reactions were rare (2%). Other mild anxiety, confusion, headache, and insomnia were more frequent with the addition of TTFields to temozolomide but occurred mostly at initiation of therapy²⁴. The risk of seizures was not increased with the addition of TTFields. Thus, TTFields has been shown to be safe in large trials with glioblastoma patients in combination with adjuvant temozolomide. However, in EF-14, the patients did not start TTFields until after radiation therapy. There have been no clinical trials to date using TTFields during radiotherapy with concurrent temozolomide. In preclinical studies, glioma cells that had been treated with the combination of radiation therapy (RT) and TTFields exhibited a greater fraction of double strand breaks with aberrant DNA damage repair compared with either modality alone²⁸. Given the synergism with RT, combined treatment may increase the efficacy of TTFields therapy to enhance its proven survival benefit for patients with newly diagnosed GBM.

There are certain technical and safety considerations if patients are to be treated with electrodes in place. During TTFields therapy, patients are allowed brief periods unplugged from the device. In the general course of radiation therapy, the actual delivery of radiation dose at each treatment visit is no more than 15 minutes. Patients can thus turn off and unplug their TTFields device while undergoing radiotherapy with the electrodes remaining in place to prevent possible interference and damage to their device. Studies of radiation therapy in patients with cardiac devices, such as pacemakers and defibrillators, have shown that we can expect a certain amount of electromagnetic noise created by RT delivery, that while potentially detrimental to circuit boards, RAM, and transistors^{29,30}, are unlikely to produce permanent damage to simpler components such as wiring and electrodes. With the array adherent to the scalp, one has to consider potential interference with the radiation dosimetry (See *Study Design*) and possible interference with the sculpting of a high-quality radiation mask. Given that a small degree of attenuation is likely, we will perform measurements for reference.

Treatment-associated inflammation, edema, or necrosis is a known risk of radiation therapy and temozolomide, occurring in a percentage of patients with newly-diagnosed glioblastoma undergoing standard therapy, with some series reporting 14 out of 51 patients having MRI or pathological evidence of this phenomenon (the true incidence remains uncertain due to difficulties in imaging interpretation).³¹ This is often an asymptomatic and self-limited process which can be mitigated with corticosteroids. The addition of TTFields to concurrent radiation and temozolomide chemotherapy has not been tested. However, per the EF-14 trial, in which TTFields was started only 4 weeks after radiation and combined with adjuvant temozolomide, there was no significant increase in treatment associated effects. The standard of care requires a post-radiation therapy MRI scan approximately 4 weeks after completing initial chemoradiation, included also in our study, which can identify treatment-related effects that can be treated with corticosteroid therapy. If this process is excessive, requiring more than 8mg of dexamethasone daily for 7 consecutive days or produce significant neurologic dysfunction, then treatment may be discontinued per investigator judgment for patient safety. Beyond the risks of study therapy exposure, other risks of study participation include additional visits and examinations, vital signs, blood draws for screening and for toxicity evaluation during the radiation period. Otherwise, MRI scans and quantity of subsequent visits, radiation and temozolomide chemotherapy received are the same as the standard of care.

Alternatives to this intervention include proceeding with the standard of care treatments and procedures for glioblastoma. Although the use of TTFields in the adjuvant setting has improved the survival for newly diagnosed patients, the prognosis remains poor, which is the rationale for conducting this trial.

The potential benefits of the therapy are promising. Tumor treating fields have improved survival for patients with newly diagnosed glioblastoma when added to temozolomide as maintenance therapy after standard chemoradiation. This has led to a modest but true benefit in overall survival on the order of months, leading to FDA approval of the device for use in newly diagnosed patients. Emerging preclinical data suggests that TTFields acts not only through disruption of mitotic apparatus but may lead to impairment of DNA repair and increased DNA double strand breaks in tumors after recent irradiation. TTFields has been used concurrently with TMZ and proven to be safe and well-tolerated as a maintenance therapy after radiation, but has not been used in combination with TMZ during radiation.

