- 4. Investigator judgment, safety** – Investigator may discontinue treatment due to concerns of safety. This includes significant neurological decline during treatment or requirement of steroids beyond the daily limit of 8mg of dexamethasone or bioequivalent dose for more than 7 consecutive days.
- 5. Lack of compliance** - The Sponsor or investigator may remove a patient from study therapy for lack of compliance to the study protocol. Patients who are using the TTField treatment less than 75% of the minimum recommended usage of 18 hours a day on average, as assessed monthly (13 hours a day or less), unless per officially instituted dose reduction, may be discontinued at the discretion of the investigator or sponsor.
- 6. Inter-current illness** – Illness that prevents further administration of treatment.

Enrollment Plan

a) Anticipated Start Date

- Dosimetric testing and analysis planned for September, 2019.
- Screening planned to begin November, 2019.

b) Total Expected Duration of the Clinical Trial

Anticipated duration of the trial will be 36 months from start of screening to completing two year long-term follow of the last patient enrolled.

c) Expected Duration of Each Subject's Participation

Up to 24 months from subject screening date to the point of study discontinuation based on specified criteria above or completion of the clinical trial.

e) Estimated Time Needed to Select the Required Number of Subjects (i.e., Enrollment Period)

The anticipated initial enrollment period for the 6 subjects in the lead-in cohort will be 4-8 weeks, with 3 subjects from each of the 2 study sites.

Following the interim analysis of safety for the lead-in cohort, there will be an expansion of enrollment to 15 patients, followed by another safety stop and interim analysis. The final cohort will comprise a total of 30 patients between the 2 participating sites. At least 1/3 of the subjects will be enrolled from each of the 2 study sites to ensure even enrollment (i.e., at least 10 subjects at each site). Anticipated duration for subject enrollment will be 6 to 12 months from start of screening to last subject enrolled in study.

Clinical Trial-Related Procedures

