7. SUBJECT ASSESSMENTS FOR SAFETY AND EFFICACY

The study procedure calendar for this study is provided in **Appendix 3**.

a) Evaluation of Safety and Tolerability**Dose Limiting Toxicity**

Dose limiting toxicities (DLTs) are defined as any severe or life-threatening treatment-related toxicity that precludes the use of a specified dose of any of the study treatments (TTFields, temozolomide, radiation) including continued use of Optune TTFields device at the standard treatment levels and schedule set out by prior studies. This study will prioritize preserving the standard of care for glioblastoma using approved dosing and radiation of temozolomide and radiation.

Toxicities will be graded according to the CTCAE (Version 5.0) scale. If multiple toxicities are seen, the presence of DLT should be based on the most severe toxicity experienced. Dose-limiting toxicities will be defined as any of the following events which occur during the experimental trimodal therapy with TTFields is added concurrently to radiation and temozolomide therapy or during the 8 weeks after RT is completed, and are considered by the investigator to be attributable to TTFields or the combination of TTFields with radiation and/or temozolomide:

- Any Grade > 3 thrombocytopenia, and Grade 4 anemia and neutropenia.
- Any nonhematologic Grade > 3 toxicity (including nausea, vomiting, or diarrhea), excluding alopecia.

- Any Grade 3-4 radiation-induced skin changes that persist for greater than 7 days and does not improve with management recommendations as outlined in toxicity management.
- Any adverse effect deemed by the investigator, patient's primary neuro-oncologist, or radiation oncologist to be life threatening in nature.

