Progression	Defined by any of the following: Greater than or equal to 25% increase in sum of the products of perpendicular diameters of enhancing lesions compared with the smallest tumor measurement obtained either at baseline (if no decrease) or best response, on stable or increasing doses of corticosteroids*; significant increase in T2/FLAIR nonenhancing lesions on stable or increasing doses of corticosteroids compared with baseline scan or best response after

	initiation of therapy* not cause by comorbid events (eg, radiation therapy, demyelination, ischemic injury, infection, seizures, post-operative changes, or other treatment effects); any new lesion; clear clinical deterioration not attributable to other causes apart from the tumor (eg, seizures, medication adverse effects, complications of therapy, cerebrovascular events, infection, and so on) or changes in corticosteroid dose; failure to return for evaluation as a result of death or deteriorating condition; or clear progression of non-measurable disease.
--	--

Evaluation of Pseudoprogression

Pseudoprogression is defined as worsening of the MRI lesions (enhancing lesion, T2/FLAIR hyperintense nonenhancing lesions) as a result of effects other than tumor growth. These can be the result of treatment effects from radiation, TTFields therapy, or chemotherapy, or changes in the steroid dose. Pseudoprogression is typically self-limited and suggests different clinical implications from true progression of the brain tumor. However, clinically and radiographically, pseudoprogression and tumor progression are difficult to distinguish.

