MRIs in this study will be evaluated centrally by the principal investigator according to RANO criteria and definitions and need to account for possible pseudoprogression from any of the treatments. Therefore, in this trial, if a subject has an MRI scan concerning for progression without substantial neurological symptoms or signs within 6 months of starting TTFields therapy, it is recommended that the subject continue therapy and obtain a follow-up scan approximately 4 weeks apart to confirm progression. If that follow-up scan confirms progression, the patient shall be taken off the study treatments. If that scan is stable when compared to the prior scan, then pseudoprogression will be noted and treatment will continue. If a subject whose scan is concerning for progression also develops substantial neurological decline, or requires increasing steroid dose beyond the daily limit of 8mg dexamethasone for more than 4 weeks, then no confirmatory scan is needed; progression will be noted and that subject shall be discontinued from the study treatments. Similarly, no confirmatory scan is needed if a subject develops MRI changes concerning for progression with or without substantial neurological decline after 6 months of initiating TTFields therapy.

Reporting of Adverse Events

Evaluation of Safety

Analyses will be performed for all patients having received at least one day of TTFields therapy. The study will use the CTCAE v5.0 for reporting of non-hematologic adverse events and modified criteria for hematologic adverse events, see Section 7a (Subject assessments for evaluation of safety and tolerability).

There will not be a formal Study Chair. There will be three DSMC members who will share the responsibility of monitoring study conduct and safety across participating sites.

Definitions of Adverse Events

Adverse Event

An adverse event (also known as an adverse experience) is defined as any untoward medical occurrence associated with the use of a medical device in humans, whether or not considered device related. More specifically, an adverse event (can be any unfavorable and unintended sign (e.g., an abnormal laboratory finding), symptom, or disease temporally associated with the use of a device, without any judgment about causality. An adverse event can arise from any use of the device (e.g., off-label use, use in combination with another treatment or drug).

Adverse reaction

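### Symptomatic treatment effect on the brain can be recorded as unconfirmed tumor progression, and the plan does not require it to be assessed separately as toxicity

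*Combined protocol and SAP*

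**What the plan says.** **As a safety matter.** Section 4 describes treatment-associated inflammation, edema or necrosis as a known risk of chemoradiation, untested with TTFields added. Its trigger for the severe form reads: "If this process is excessive, requiring more than 8mg of dexamethasone daily for 7 consecutive days or produce significant neurologic dysfunction". The consequence that it attaches is discretionary: "then treatment may be discontinued per investigator judgment for patient safety". Section 6, Criteria for Removal from Study Therapy, places significant neurological decline and "requirement of steroids beyond the daily limit of 8mg of dexamethasone or bioequivalent dose for more than 7 consecutive days" under the safety criterion. Progression is a separate criterion.

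**As progression.** Section 7b, Evaluation of Pseudoprogression, recommends a follow-up scan about 4 weeks later for a patient whose scan worsens within 6 months of starting TTFields without substantial neurological symptoms. A different rule covers a patient who "also develops substantial neurological decline, or requires increasing steroid dose beyond the daily limit of 8mg dexamethasone for more than 4 weeks". For that patient the instruction is: "then no confirmatory scan is needed; progression will be noted and that subject shall be discontinued from the study treatments".

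**Against a progression call.** The RANO table in Section 7b counts "clear clinical deterioration not attributable to other causes apart from the tumor" and lists complications of therapy among those other causes. It also excludes T2/FLAIR change caused by radiation or other treatment effects. The pseudoprogression text names TTFields as a possible cause, tells the central reader to allow for it, and concedes that "clinically and radiographically, pseudoprogression and tumor progression are difficult to distinguish".

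**Link to the primary endpoints.** These count treatment-related events and DLTs. Section 7a requires a DLT to be "considered by the investigator to be attributable to TTFields or the combination of TTFields with radiation and/or temozolomide". Section 8 plans no count of pseudoprogression or treatment effect.

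**The concern.** The follow-up scan is the plan's one procedure for telling treatment effect from tumor early on. It is recommended for patients without substantial symptoms and is not required for those with them. The most severe cases are thus the ones most likely to carry a progression label that nothing later tests.

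The trial asks whether adding TTFields to chemoradiation is safe. If the combination increases symptomatic edema or necrosis, part of that signal could appear as early progression instead of toxicity. The first scheduled post-radiation MRI falls inside the DLT window, so the overlap sits where the lead-in decisions are made. No sentence says whether an event noted as progression must also be assessed as a treatment-related event or DLT, and Section 8 offers no table from which a reader could see such a shift.

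**Working it through.** **1. The texts side by side** (scan worsening within 6 months of starting TTFields)

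| Presentation | Sections 4 and 6 | Section 7b, pseudoprogression text | RANO table |
|---|---|---|---|
| Significant or substantial neurological decline | Safety; treatment may stop | Progression noted, no confirming scan, treatment stops | Not clinical progression if due to complications of therapy |
| Above 8 mg for more than 4 weeks | Safety; treatment may stop | Progression noted, no confirming scan, treatment stops | Deterioration due to steroid change, and T2/FLAIR change due to treatment effect, excluded |
| Above 8 mg for 7 days up to 4 weeks, no substantial symptoms | Safety; treatment may stop | Follow-up scan recommended | As above |

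The first two rows fall under both the safety wording and the progression rule. The third does not. The steroid part of Section 4's trigger therefore does not by itself activate the Section 7b rule; neurological dysfunction with a worrying scan does. Section 4 says 7 consecutive days, Section 6 more than 7, and Section 7b more than 4 weeks.

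**2. Timing.** The first on-treatment MRI is on Day 78 ± 5, and the DLT window closes with the Day 106 ± 5 visit, which reuses that MRI. The next recommended MRI is at Cycle 3 Day 1: 106 + 28 = Day 134. No routine scan can resolve a Day 78 finding before the window closes.

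**3. Route to the safety counts.** Under Recording of an Adverse Event, all grade 3 and higher events are entered whatever their attribution. To reach the primary endpoint an event must also be judged related. An investigator who has recorded progression may choose Unlikely, because the patient's clinical condition explains the event. The category Possible counts as related and also covers events that the clinical condition could have produced. Either choice is open.

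**4. Route to PFS.** The plan does not define a PFS event. Section 6, Maintenance TTField therapy, has sites document the date of confirmed progression, while Section 7b notes progression without confirmation. Whether these cases count is undetermined.

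**5. The figure the plan gives.** Section 4 cites 14 of 51 patients on standard therapy: 14/51 = 27.5%, exact (Clopper-Pearson) 95% CI 15.9% to 41.7%. In 30 patients that is 30 × 0.2745 = 8.2. It covers any severity without TTFields. The documents give no rate for severe cases or for cases attributable to TTFields.

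**6. Sensitivity of the rules.** One patient is 1/6 = 16.7 points of the first lead-in DLT rate, 1/15 = 6.7 of the second, and 1/30 = 3.3 of the final DLT rate or PFS6. Binomial stopping probabilities at assumed recorded DLT rates, each rule taken alone:

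| Recorded DLT rate | P(2 or more of 6) | P(5 or more of 15) |
|---|---|---|
| 5% | 3.3% | 0.1% |
| 10% | 11.4% | 1.3% |
| 20% | 34.5% | 16.4% |

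For example, P(2 or more of 6) at 10% = 1 − 0.9^6 − 6 × 0.1 × 0.9^5 = 0.114. The table shows how strongly the rules depend on what is recorded. It does not estimate how many events would be misclassified.

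**The case against.** A reader might infer that the worst toxicity of the combination must be scored as progression, drops out of the primary safety endpoint, and biases PFS6 downward. The documents do not support that.

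- Nothing removes an event from the safety data because progression was noted. Grade 3 and higher events are entered regardless, the DSMC reviews all SAEs, and one event can be both an adverse event and a progression. Section 6 also gives grade 3-4 neurologic symptoms a toxicity route that can end in a DLT.
- Ambiguous edema versus tumor fits the attribution category Possible, which counts as related.
- Section 7b also tells the reader of the MRI to allow for pseudoprogression. The text contradicts itself; it does not simply compel a progression call.
- With PFS events undefined and Section 6 referring to confirmed progression, a downward bias is an inference. PFS6 is secondary and not powered.

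It is also tempting to feed 14/51 into the stopping rules. That would add background events seen without TTFields as if they were attributable to it, treat every symptomatic case as a DLT although Section 7a asks for nonhematologic toxicity above grade 3 or a life-threatening effect, and place every case inside the window.

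All of these objections stand. They reduce the concern from a certain loss to a possible one. They leave in place the conflict between sections and the missing requirement for an independent toxicity assessment.

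**Conclusion.** The concern holds in limited form. For a worrying scan with substantial neurological decline (or more than 4 weeks above 8 mg dexamethasone) within 6 months of starting TTFields, the plan gives conflicting instructions with no order of priority. Symptomatic treatment effect can be recorded as progression, may be attributed to disease and so missed in the treatment-related and DLT counts, and may enter PFS.

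How often this would happen cannot be stated: it depends on investigator attribution and on a rate of severe cases that the documents do not give. With the stopping thresholds at 2 of 6 and 5 of 15, a change in the classification of one or two patients can change a lead-in decision. That is sufficient reason to settle the wording before the interim reviews.

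**What to change.** 1. **Reconcile the texts.** Bring Section 4, the removal criteria in Section 6, the RANO table and the pseudoprogression text in Section 7b into agreement, including 7 days versus 4 weeks, discretionary versus mandatory stopping, and the reference to confirmed progression in Section 6. Which clinical rule should apply is for the sponsor and investigators; none is proposed here.
2. **Separate toxicity from the progression call.** State that any such event in the DLT window is graded by CTCAE and attributed for the treatment-related and DLT counts, whether or not progression is also noted. There should be no default presumption of DLT. Since the next routine MRI falls after the window, a presumption could count true early progression toward the 2-of-6 rule, and Section 7a discontinues any patient with a DLT.
3. **Define the PFS event.** Flag progression noted without confirmation within 6 months as unconfirmed. Report PFS6 with and without these cases as events, using later routine MRIs where available.
4. **Add a table** of symptomatic and asymptomatic pseudoprogression or treatment effect, each with an exact 95% CI.

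The cost is protocol and SAP wording, one table and one sensitivity analysis, with no added scans. Some cases will stay unresolved, because follow-up after stopping treatment is voluntary.
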